2.0 SPECIFIC AIMS

This randomized controlled trial (RCT) aims to treat youths ages 12- to 17-years-old who have a current diagnosis of a depressive disorder or high levels of depressive symptoms (CDRS-R ≥ 35). The aim is to test the effects of CBT+SCT for (1) increasing children's social cognitive (SC) abilities. We also will examine the effects of the treatments on reducing depressive symptoms.

Hypothesis: Adolescents receiving CBT+SCT will show significantly higher levels of SC abilities at post-intervention, controlling for pre-intervention levels, as compared to youth in CBT alone.

Exploratory Hypothesis: Youth in CBT+SCT will show significantly lower levels of depressive symptoms at post-intervention, controlling for baseline levels, as compared to youth in CBT only.

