8.0 Statistical Analysis Plan

We will use the general linear model (i.e., MANCOVA) to test hypotheses. The between subjects factor will be *Condition* with two levels (CBT+SCT vs. CBT only) and the within-subjects factor will be Time with two levels (baseline, post-test). We will adopt a multivariate approach to repeated measures (as assumptions of compound symmetry are untenable). Dependent variables (DVs) will vary across analyses; child age and sex, will be covariates in all analyses.

Specific Aims. To test whether youth in CBT+SCT have better SC skills at post-treatment than youth in CBT only at post-treatment.

Hypothesis: We will test the effect of CBT+SCT on SC skills (target) using the *Faux Pau* task as the DV. We will first test the 2x2 Condition x Time interaction. We expect that a 2x2 partition of this interaction will be significant, reflecting the Condition effect from baseline to post-test.

Exploratory Hypothesis: To test the effect of CBT+SCT on depressive symptoms, the DV will be the clinician-rated depression measure (CDRS). Analyses will be the same as described for the main hypothesis except that we will test the depression measure as the dependent variable.

Power. To estimate power, we assumed that autocorrelations among the repeated measures were .4 - .6. With N=42 (21 per cell), alpha = .05, and a medium effect size (e.g., a .40 SD Condition effect at T2), we will have approximately .82 power to detect the initial 2x2 Condition x Time interaction ($f_v = .32$). Assuming correlations of .3-.6 among the same measure over time, alpha = .05, and medium effect sizes we will have .85 power for the 2x2 Condition by Time interaction.

9.0 Privacy/Confidentiality Issues: Methods for protecting privacy and confidentiality.

All research data will be coded with a study ID number rather than names. No identifying information will be stored with research data. A database linking participant contact information to study ID numbers will be password-protected and stored on a secure server. Only key study personnel involved in contacting participants will have access to this information. Questionnaire data will be collected and stored online.

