STUDY TITLE: Mind over Mood

R61 PHASE: Social Cognitive Training to Enhance the Efficacy of CBT for Depression in Youth:
A Developmental Approach

STUDY IRB NUMBER # 190077

PRINCIPAL INVESTIGATOR

[name]., Vanderbilt University, Department of Psychology and Human Development

SPONSOR NAME

National Institutes of Health (NIH)
NIH Grant/Sponsor # R61 MH115125

VERSION DATE: SAP adapted from the IRB Application approved on 06/02/2019

ClinicalTrials.gov Identifier: NCT03954392

Statistical Analysis Plan

We will use the general linear model (i.e., MANCOVA) to test hypotheses. The between subjects factor will be *Condition* with two levels (CBT+SCT vs. CBT only) and the within-subjects factor will be Time with two levels (baseline, post-test). We will adopt a multivariate approach to repeated measures (as assumptions of compound symmetry are untenable). Dependent variables (DVs) will vary across analyses; child age and sex, will be covariates in all analyses.

Specific Aims. To test whether youth in CBT+SCT have better SC skills at post-treatment than youth in CBT only at post-treatment.

Hypothesis: We will test the effect of CBT+SCT on SC skills (target) using the *Faux Pau* task as the DV. We will first test the 2x2 Condition x Time interaction. We expect that a 2x2 partition of this interaction will be significant, reflecting the Condition effect from baseline to post-test.

Exploratory Hypothesis: To test the effect of CBT+SCT on depressive symptoms, the DV will be the

clinician-rated depression measure (CDRS). Analyses will be the same as described for the main hypothesis except that we will test the depression measure as the dependent variable.

Power. To estimate power, we assumed that autocorrelations among the repeated measures were .4 - .6. With N=42 (21 per cell), alpha = .05, and a medium effect size (e.g., a .40 SD Condition effect at T2), we will have approximately .82 power to detect the initial 2x2 Condition x Time interaction ($f_v = .32$). Assuming correlations of .3-.6 among the same measure over time, alpha = .05, and medium effect sizes we will have .85 power for the 2x2 Condition by Time interaction.

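### The stated power of .82 does not follow from the plan's own inputs: at N=42 a .40 SD effect gives .21–.29 (.28–.35 by ANCOVA), f_v = .32 gives .53, and the .85 figure is unsupported

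*Protocol*

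**What the plan says.** The power paragraph is the same in protocol section 8.0 and in the SAP. It sets the size and significance level ("With N=42 (21 per cell), alpha = .05") and assumes pre-post correlations of .4 to .6. The effect and the claimed power are given together: "a medium effect size (e.g., a .40 SD Condition effect at T2), we will have approximately .82 power to detect the initial 2x2", where the test meant is that of condition by time. The effect is also expressed on a second scale: "Condition x Time interaction ($f_v = .32".

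A second sentence then reads "Assuming correlations of .3-.6 among the same measure over time, alpha = .05, and medium effect sizes we will have .85 power" for the same interaction. It gives no number for the effect and does not restate N.

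The analysis is a 2 x 2 repeated-measures model with age and sex as covariates. Protocol section 2.0 words the main hypothesis differently, as a baseline-adjusted comparison: "significantly higher levels of SC abilities at post-intervention, controlling for pre-intervention levels, as compared to youth in CBT alone". Neither document states sidedness, a dropout allowance, the variance expected to be explained by the covariates, or the power formula.

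**The concern.** The paragraph links five quantities: N, the .40 SD effect, the correlation range, f_v and the power. Any three of N, effect, correlation and power fix the fourth, and f_v follows from the effect and the correlation. A difference of .40 SD with 21 per arm is a modest effect in a small trial, and correlations of .4–.6 do not reduce the variance of change enough to bring power near .8. The second sentence lowers the bottom of the correlation range, which reduces power, yet claims more of it.

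This is the only sample-size justification in either document, and it supports the main, non-exploratory hypothesis on the Faux Pas task. A reader who believes there is .82 power for .40 SD would take a non-significant result as fair evidence against an effect of that size.

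**Working it through.** **Inputs from the documents:** 21 per arm; alpha .05; .40 SD at post-test; f_v = .32; r = .4–.6 (first sentence) and .3–.6 (second); stated power .82 and .85.

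**Assumptions, because the documents are silent:** two-sided test; no dropout; age and sex explain no variance; equal expected baselines (randomised); equal SDs at both times; the .40 SD is in raw-score SD units; f_v is scaled so that the noncentrality is λ = N × f_v².

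**1. The planned test at .40 SD.** With two time points the interaction is a t-test on change scores with 40 df, so the multivariate approach does not alter it. In raw-score SD units:

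- SD of change = √(2(1−r))
- d = .40 / SD of change, and f_v = d/2
- noncentrality = d × √(21/2)

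| r | SD of change | d | f_v | noncentrality | power |
|---|---|---|---|---|---|
| .4 | 1.095 | .365 | .183 | 1.183 | .211 |
| .5 | 1.000 | .400 | .200 | 1.296 | .244 |
| .6 | .894 | .447 | .224 | 1.449 | .293 |

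The stated .82 is not reproduced. A simulation of 20,000 trials gave .214 at r=.4 and .291 at r=.6. Using 38 df to allow for the two covariates leaves the results essentially unchanged.

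**2. Baseline-adjusted ANCOVA, as section 2.0 words the hypothesis.** The residual SD is √(1−r²), with 37 df. Power is .281, .308 and .352 at r = .4, .5 and .6.

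**3. f_v = .32 taken directly.** λ = 42 × .32² = 4.30 on F(1, 40) gives power .526. With λ = 40 × .32² it is .506.

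**4. The two effect sizes against each other.** f_v = .32 means d = .64, which is .64 × SD of change = 0.70, 0.64 and 0.57 SD at r = .4, .5 and .6. A .40 SD difference equals f_v = .32 only if r = 1 − (.40/.64)²/2 = .80. That is outside the stated range, and power is then still only about .53.

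**5. What .82 would need at N=42.** It needs d = .909 (f_v = .455), a post-test difference of 0.996, 0.909 or 0.813 SD at r = .4, .5 or .6. At .40 SD it would need r = 1 − (.40/.909)²/2 = .90.

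**6. The .85 sentence, if N=42 applies.** Over r = .3–.6, .40 SD gives .188–.293 and .50 SD gives .267–.424. Power of .85 needs d = .948, which is 1.12 SD at r=.3 and 0.85 SD at r=.6.

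**7. What 21 per arm can deliver (r = .4, .5, .6).**

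| | Condition x Time | ANCOVA |
|---|---|---|
| Difference detectable with 80% power (SD) | .971, .886, .793 | .814, .769, .710 |
| Expected 95% CI half-width (SD) | .683, .624, .558 | .573, .542, .500 |

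The half-width is t(.975) × SD × √(2/21), with the SD of change on 40 df or the residual SD on 37 df.

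**8. Sensitivity, Condition x Time at .40 SD, r = .4–.6.**

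- One-sided alpha .05: .315–.413.
- Age and sex explaining 10% of change-score variance: .229–.319; 30%: .281–.393. Reaching .82 would need 84% (r=.4) or 76% (r=.6).
- 19 completers per arm: .195–.269; 17 per arm: .178–.244.

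**The case against.** The strongest reply is that the figures probably come from an effect-size convention rather than a slip. If a medium interaction effect f = .25 is entered with λ = f² × N × 2/(1−r), then at N=42 and r=.4 power is .823, and f/√(1−r) = .25/√.6 = .323, close to the stated f_v. At r=.45, the middle of the second range, the same convention gives .854. Other routes to about .82 are f_v = .32 with N=84 (.826) or with λ doubled (.816).

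This may explain the numbers, but it does not support them. An interaction f of .25 means cell means ±.25 SD from the additive model, so a difference in change of 4 × .25 = 1.0 SD, two and a half times the stated .40 SD. The other routes double the sample or count 84 observations as if independent. Each one breaks or goes beyond a stated input.

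Three parts of the objection do stand.

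- The arithmetic does not show which input was mistaken; the .40 SD is given only as an example of a medium effect.
- Sidedness is not stated and the hypothesis is directional. One-sided, f_v = .32 gives .65 and ANCOVA at .40 SD gives .40–.48. If age and sex also explained 30% of the variance, one-sided f_v = .32 would give .79. All remain below .82.
- A null result would not be wholly without information. With a half-width of 0.56–0.68 SD, an estimate below about −0.16 to −0.28 SD (.40 minus the half-width) would exclude .40 SD. Weakly informative is the fairer description.

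**Conclusion.** The concern holds. There are two separate contradictions: .40 SD and f_v = .32 are different effects at the stated correlations, and neither gives .82 at N=42. On the two-sided assumptions listed, the plan's own inputs give about .21–.53, depending on which stated effect size and which analysis is used. A true .40 SD effect would be missed about 71–79% of the time by the planned test (65–72% by ANCOVA), and the expected confidence interval half-width exceeds .40 SD under either analysis. The .85 figure cannot be reproduced as written. No variant examined that keeps the stated N, effect size and correlations comes near .82 without an implausible contribution from age and sex. The statement is wrong as it stands and must be corrected, because it is the trial's only sample-size justification.

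**What to change.** In both protocol section 8.0 and the SAP, replace the two power sentences with one statement for the planned test. For example: *With 21 per arm, two-sided alpha .05, pre-post correlation .4–.6, no dropout and no variance explained by age and sex (all assumed), power of the Condition x Time test for a .40 SD difference at post-test is about .21–.29; the difference detectable with 80% power is 0.79–0.97 SD; the expected 95% CI half-width is 0.56–0.68 SD.* If baseline-adjusted ANCOVA is named as the primary analysis, the corresponding figures are .28–.35, 0.71–0.81 SD and 0.50–0.57 SD.

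Delete f_v = .32 and the .85 figure. If the investigators had a larger effect in mind, they should state it as a post-test difference in SD units, with sidedness and the formula used. Report the result as an estimate with its 95% CI, so that the precision is visible whatever the p-value.

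The cost is a wording change in two documents and a much less favourable power statement. The correction needs no added participants, and it does not settle whether N=42 is adequate.

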STUDY TITLE: Mind over Mood

R61 PHASE: Social Cognitive Training to Enhance the Efficacy of CBT for Depression in Youth:
A Developmental Approach

STUDY IRB NUMBER # 190077

PRINCIPAL INVESTIGATOR

[name]., Vanderbilt University, Department of Psychology and Human Development

SPONSOR NAME

National Institutes of Health (NIH)
NIH Grant/Sponsor # R61 MH115125

VERSION DATE: SAP adapted from the IRB Application approved on 06/02/2019

ClinicalTrials.gov Identifier: NCT03954392

Statistical Analysis Plan

We will use the general linear model (i.e., MANCOVA) to test hypotheses. The between subjects factor will be *Condition* with two levels (CBT+SCT vs. CBT only) and the within-subjects factor will be Time with two levels (baseline, post-test). We will adopt a multivariate approach to repeated measures (as assumptions of compound symmetry are untenable). Dependent variables (DVs) will vary across analyses; child age and sex, will be covariates in all analyses.

Specific Aims. To test whether youth in CBT+SCT have better SC skills at post-treatment than youth in CBT only at post-treatment.

Hypothesis: We will test the effect of CBT+SCT on SC skills (target) using the *Faux Pau* task as the DV. We will first test the 2x2 Condition x Time interaction. We expect that a 2x2 partition of this interaction will be significant, reflecting the Condition effect from baseline to post-test.

Exploratory Hypothesis: To test the effect of CBT+SCT on depressive symptoms, the DV will be the

clinician-rated depression measure (CDRS). Analyses will be the same as described for the main hypothesis except that we will test the depression measure as the dependent variable.

Power. To estimate power, we assumed that autocorrelations among the repeated measures were .4 - .6. With N=42 (21 per cell), alpha = .05, and a medium effect size (e.g., a .40 SD Condition effect at T2), we will have approximately .82 power to detect the initial 2x2 Condition x Time interaction ($f_v = .32$). Assuming correlations of .3-.6 among the same measure over time, alpha = .05, and medium effect sizes we will have .85 power for the 2x2 Condition by Time interaction.
